#### **4.2.5.3 Handling of Dropouts and Missing Data**

All available data on hospital admissions and ED visits are to be used irrespective of intercurrent events. For the primary analysis, no adjustment is made for dropout but the sensitivity of the results to this approach are investigated using a sensitivity analysis in section 4.2.5.5.

#### **4.2.5.4 Primary Analysis of Secondary Endpoint #3**

A descriptive summary (Mean, SD, Median, Range) of the number of all-cause hospital admissions or ED visits with HK as a contributing factor will be presented by randomised treatment group in the FAS. A negative binomial regression model will be conducted with the number of all-cause hospital admissions or ED visits with HK as a contributing factor as the dependent variable and randomised treatment group (reference level SoC) as the independent variable. The duration of time per participant in study is calculated until the earliest of loss to follow-up or 180 days post-discharge and will be included in the model as an offset term. The incidence rate ratio (SZC/SoC), along with 95% CIs and two-sided p-values will be displayed.

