## **Outpatient Period**

The outpatient period refers to the period from the date of randomisation until the earliest date of end of treatment, withdrawal of consent, last contact with the participant or death (inclusive).

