#### **4.2.3.3 Handling of Dropouts and Missing Data**

Participants who are lost to follow-up will be censored at the date of discontinuation as recorded on the participant's disposition form.

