#### **4.2.4.2 Derivations**

Time to first occurrence will be defined as the earliest date of (all-cause hospital admission, ED visits with HK as a contributing factor, all-cause death, use of rescue therapy for HK, date of loss to follow-up, date of 180 days post-discharge) – date of randomization + 1.

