#### **4.2.5.1 Definition**

- Population: Full analysis set
- Endpoint: Number of all-cause hospital admissions or ED visits with HK as a contributing factor at any time post-discharge up to 180 days.
- Intercurrent event strategy: Participants who discontinue treatment, use rescue therapy for HK or who have an ED visit without HK as a contributing factor, will continue to be followed up to the first component of the composite endpoint (treatment policy

strategy). Participants who die of any cause or are lost to follow-up will be censored at the date of death or loss to follow-up. Participants who have RAASi down-titration (including discontinuation) will continue to be followed up to the first component of the composite endpoint (treatment policy strategy).

- Population level summary (analysis): Mean number of all-cause hospital admissions or ED visits, with HK as a contributing factor by randomised treatment group. Negative binomial regression model with randomised treatment group as the independent variable and including duration of time in study as an offset. The incidence rate (SZC/SoC), along with 95% confidence intervals and two-sided p-values will be displayed.

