#### **4.2.6.2 Derivations**

Time to first occurrence will be defined as the earliest date of (date of RAASI down-titration (or discontinuation), all-cause death, date of loss to follow-up, date of 180 days post-discharge) – date of randomization + 1.

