#### **4.2.8.4 Primary Analysis of Secondary Endpoint #6**

The primary analysis of this secondary endpoint will be performed as per section 4.2.5.4.

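### The exposure offset for SAP secondary endpoints #3 and #6 omits death, although both estimands censor at death

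*SAP*

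**What the plan says.** The estimand for SAP secondary endpoint #3 (4.2.5.1) states: "Participants who die of any cause or are lost to follow-up will be censored at the date of death or loss to follow-up". SAP 4.2.8.1 has the same sentence for #6, and protocol 9.4.3.2 says the same for its secondary endpoints #3 and #5 (protocol #5 is SAP #6). Both estimands specify a negative binomial model with time in study as the offset.

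The only explicit rule for computing that time is in 4.2.5.4: "The duration of time per participant in study is calculated until the earliest of loss to follow-up or 180 days post-discharge". SAP 4.2.8.4 carries it over to #6: "The primary analysis of this secondary endpoint will be performed as per section 4.2.5.4".

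SAP 4.2.5.3, with the same wording in 4.2.8.3, adds: "All available data on hospital admissions and ED visits are to be used irrespective of intercurrent events".

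The endpoints stand fourth and seventh in the testing order of SAP Table 5.

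**The concern.** The estimand stops follow-up at death, but the offset rule does not. A participant who dies would be credited with exposure up to Day 180, including days on which no admission can occur. Each arm's rate is then understated in proportion to the person-time it loses to death. If the losses differ, the rate ratio is biased in favour of the arm that loses more. That is the arm with more deaths only when deaths occur at similar times.

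The sensitivity analyses in 4.2.5.5 would not expose this. The covariate-adjusted model uses time in study as its offset too, and the per protocol analysis repeats the main method. The mean cumulative count analysis runs only if loss to follow-up, not death, differs by more than 10% between arms.

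The all-available-data statement creates a second, smaller mismatch. Events recorded after loss to follow-up but before Day 180 would enter the count with no matching exposure, although the estimands censor there.

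**Working it through.** **1. Can loss to follow-up be read as including death?** No.
- Protocol 7.3 defines loss to follow-up as failed contact that leaves the participant's status unknown.
- The estimand sentences name death and loss to follow-up separately.
- The SAP's time-to-event derivations list both as separate end dates: "all-cause death, use of rescue therapy for HK, date of loss to follow-up, date of 180 days post-discharge" in 4.2.4.2 and "all-cause death, date of loss to follow-up, date of 180 days post-discharge" in 4.2.6.2. SAP 4.2.3.2 and 4.2.7.2 do likewise.
- SAP 3.3.1.2 ends the outpatient period at death, which suggests an oversight. But the offset sentence gives its own list and does not refer to that period.

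**2. Effect on one participant.** One admission, then death on Day 30: true exposure is 30 days, literal exposure 180 days, and 180/30 = 6.

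**3. Effect on the rate ratio.** The plan gives no figure to reproduce and no mortality rate, so every rate below is an assumption. With m the 180-day mortality and t the mean day of death, the share of person-time lost in an arm is l = m × (1 − t/180), which is m/2 for deaths spread evenly. The SZC/SoC ratio is multiplied by (1 − l for SZC)/(1 − l for SoC).

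| Mortality SZC / SoC | Timing | Multiplier |
|---|---|---|
| 2% / 4% | even | 0.990/0.980 = 1.010 |
| 5% / 8% | even | 0.975/0.960 = 1.016 |
| 5% / 10% | even | 0.975/0.950 = 1.026 |
| 5% / 15% (upper case) | even | 0.975/0.925 = 1.054 |
| 10% / 5% | even | 0.950/0.975 = 0.974 |
| 15% / 5% | even | 0.925/0.975 = 0.949 |
| equal | equal | 1.000 |
| 5% / 8% | Day 20 / Day 150 | 0.9556/0.9867 = 0.968 |
| 8% / 8% | Day 45 / Day 135 | 0.94/0.98 = 0.959 |

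The last two rows show that timing alone can reverse or create the bias. A constant death hazard in place of even timing gives nearly the same values: 1.027 for 5%/10% and 1.056 for 5%/15%.

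Simulation agrees. With no treatment effect, 65 per arm, a mean of 0.5 events per 180 days, dispersion 1 and deaths independent of event rate, the ratio of literal-offset to death-censored estimates was 1.025 (5%/10%, even), 1.015 (5%/8%, even), 0.968 (5% at Day 20 / 8% at Day 150) and 0.959 (8% at Day 45 / 8% at Day 135).

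**4. Size against sampling error.** About 130 participants are randomised (protocol 4.1), so 65 per arm. With dispersion k and event-free proportion P0, the mean count is mu = (P0^(−k) − 1)/k, and SE = sqrt[(1/mu_SZC + k)/65 + (1/mu_SoC + k)/65].
- **#3**, with P0 = 0.83 and 0.568 from protocol 9.2.2: at k = 1, mu = 0.205 and 0.761, and SE = sqrt[(4.88 + 1 + 1.31 + 1)/65] = 0.355. For k = 0.5 and 2 it is 0.343 and 0.380. A multiplier of 1.026 (log 0.0257) is about 0.07 SE, and 1.054 (log 0.0527) is 0.14 to 0.15 SE.
- **#6**: the documents give no rate for this endpoint. Assuming 3% to 8% of SZC and 10% to 20% of SoC participants have any event, SE is 0.51 to 0.83. Then 1.026 is 0.03 to 0.05 SE and 1.054 is 0.06 to 0.10 SE.

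**5. All-available-data statements.** Assume evenly timed drop-out w, with half of later admissions still recorded. The rate is inflated by (1 − w/2 + 0.5 × w/2)/(1 − w/2).
- w = 20% in both arms: 0.95/0.90 = 1.056 in each, so the ratio is unchanged.
- 15% SZC / 25% SoC: 1.041/1.071 = 0.971.
- Reversed: 1.030.

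**The case against.** The best defence is that this is a drafting slip which the surrounding text nearly resolves. The estimand three subsections earlier censors at death, the protocol agrees, and someone who has died is not in study in any ordinary sense. A careful programmer would probably add death. The documents also point to low mortality: exclusion criterion 4 removes participants with a life expectancy under 6 months, protocol 9.2.2 adds nothing for death to its assumed event rates, and the Synopsis calls death without a prior hospitalisation or emergency department visit negligible. The mortality and timing scenarios are constructed, and both endpoints come late in a fixed sequence.

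All of this bears on weight, and most of it stands: the likely effect is small and its direction unknown. It does not repair the rule. The remark on negligible deaths does not cover deaths after an admission, and it concerns death as outcome or censoring, not exposure credited afterwards. A SAP should not rely on a programmer overriding an explicit list.

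On the second mismatch, the objection is that protocol 7.3 makes data after loss to follow-up rare, because a participant whose contact is restored is no longer lost. That is fair, and the one-half recording share has no documentary basis. The wording conflict remains, since protocol 7.2 allows information from medical records for participants who consider withdrawing, and protocol 8.8.1 provides for chart review.

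**Conclusion.** The concern holds. The offset rule for SAP secondary endpoints #3 and #6 contradicts the estimands it serves, and followed literally it counts time after death as time at risk. Under assumed 180-day mortality of 2% to 15%, evenly timed, the rate ratio moves by between −5.1% and +5.4%, or not at all if both arms lose equal person-time. That is at most about 0.15 SE for #3 and 0.10 SE for #6, and the #6 figure also rests on assumed event rates. The primary and main secondary endpoints are unaffected. The correction should still be made, because both endpoints are formally tested and the change is almost free.

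Exploratory endpoints #6 and #9 share the offset wording, but their estimands place death under treatment policy. There it is a point to confirm, not a contradiction.

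**What to change.** - **SAP 4.2.5.4 (inherited by 4.2.8.4):** define exposure as ending at the earliest of death, loss to follow-up or withdrawal, or 180 days post-discharge. For loss to follow-up or withdrawal, use the disposition-form date, in line with 4.2.3.3: "Participants who are lost to follow-up will be censored at the date of discontinuation as recorded". Use the log of this exposure as the offset and count events only within it. Naming withdrawal goes slightly beyond the estimand sentence; it is needed because protocol 7.3 keeps withdrawal of consent separate from loss to follow-up.
- **SAP 4.2.5.3 and 4.2.8.3:** limit the all-available-data statement to the intercurrent events that 4.2.5.1 and 4.2.8.1 handle by treatment policy, and state that death and loss to follow-up are censored.
- **SAP 4.2.14.4 and 4.2.17.4 (exploratory #6 and #9):** confirm whether exposure stops at death and align the text with those estimands.

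The cost is one sentence, two qualifying clauses and one confirmation covering two exploratory endpoints. Death dates are already collected (protocol 8.1.2) and discontinuation dates are already used in the time-to-event analyses, so no new data are needed.

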#### **4.2.5.5 Sensitivity Analyses of the Secondary Endpoint #3**

Three sensitivity analyses will be conducted for this secondary endpoint:

- Providing there are sufficient participants within each covariate to support the analysis, an alternative population level summary using the FAS population where the negative binomial regression model will include randomised treatment group, duration of time in study as an offset and the following baseline variables: age (as a cubic spline), sex, participant recruitment country, presence of heart failure, diabetes, RAASi use, CKD

stage, and baseline  $K^+$  ( $5.0 < K^+ \leq 5.5$  versus  $5.5 < K^+ \leq 6.5$  mmol/L) as independent variables. Baseline variables will be defined as described in section 4.2.2.6.

- A sensitivity analysis will be conducted using the mean cumulative count method (MCC) (Austin et al, 2010) if a greater than 10% difference by treatment arm in the proportion who are lost to follow-up is observed. The MCC method reflects a summarisation of all events that occur in a population by a given time. The recurring event in this analysis will be hospital admission with HK as a contributing factor. The MCC will be performed by randomised treatment group in the FAS and an estimate (95% CI) of the MCC at 90 and 180 days post discharge will be presented. A figure of the MCC by randomised treatment group with 95% CI will also be displayed. SAS Code to conduct an MCC analysis is described in sections 7.1 and 7.2.
- Alternative population: As primary estimand, but the per protocol set (PPS) will be used as the population for analysis.

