#### **4.2.8.3 Handling of Dropouts and Missing Data**

All available data on hospital admissions and ED visits are to be used irrespective of intercurrent events. For the primary analysis, no adjustment is made for dropout but the sensitivity of the results to this approach are investigated using a sensitivity analysis in section 4.2.5.5.

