## 7.2 MCC.SAS

The input data should have at least the following variables. For those who had no events (events of interest or competing risk events), one line per participant. For those with events, there is one line for each individual event. So if one had event 1,2 then there are 2 lines for this participant.

```

Macro paramters:
  input:           The input dataset
  id:             The id of participants
  d_event:        Date of occurrence of events/competing risk, if censor then the date of
  censoring
  event:          The event of interest that the MCC will be calculated, 1 for the
  event Yes and 0 for No
  event_outcome:  The outcome variable, with 0 for censoring, 1 for the event of
  interest, 2,3,4... for competing risk outcomes etc.
  d_last:         The end of follow up date. --This is the same as d_event for those who
  censored.
                  For those with at non-0 in event_outcome, this is on or after the
  latest non-0 event date.
  d_dx:           The start time, In CCSS example, it is the cancer diagnosis date.
  timeQQ:         The time to event, calculated from (d_event) and the start date of each
  person.
  output:         The output dataset */
/*#####
proc sort data=&input; by &id &d_event; run;
/*Multiple SMNs.*/
data alldata;
  set &input;
  by &id;
  if first &id then first=1;

```

```

else first+1;
run;
/*output the last record for each person so we know how many events each person has*/
data last(keep=&id first);
  set alldata;
  by &id;
  if last.&id;
run;
data alldata;
  merge alldata last(rename=(first=maxN));
  by &id;
run;
/*For cumulative incidence (not MCC), only use the first event. This is the data for first
event analysis.*/
data data_1;
  set alldata(where=(first=1));
run;

proc freq data=alldata; table &event &event_outcome; run; /*This has multiple records*/
proc freq data=data_1; table &event &event_outcome; run; /*This has only the first record*/

/*In order to calculate the MCC, in the ith event, assuming there is no event before the ith
event,
and need the data for this event of each person (for those less than
the number of event, take the maximum event record). So in each data set, one person appears
only once.*/
proc SQL; select max(maxN) into: max_number from alldata; quit;
%put the maximum number of SMNs one person had is : &max_number;

%if &max_number<2 %then %do;
  %put WARNING: The maximum number of &event events one participant had is &max_number

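### For count endpoints #3 and #6, the analysis named as the check on dropout assumes loss is unrelated to outcome and will usually not be run

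*SAP*

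**What the plan says.** Endpoint numbers follow the SAP. The protocol (9.4.3.2) numbers the second count endpoint #5.

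- **Endpoint.** SAP 4.2.5.1 defines #3 as "Number of all-cause hospital admissions or ED visits with HK as a contributing factor at any time post-discharge up to 180 days". On loss and death it says "Participants who die of any cause or are lost to follow-up will be censored at the date of death or loss to follow-up".
- **Main model.** SAP 4.2.5.4 fits a negative binomial model with log follow-up as offset: "The duration of time per participant in study is calculated until the earliest of loss to follow-up or 180 days post-discharge".
- **Dropout.** SAP 4.2.5.3 says "no adjustment is made for dropout but the sensitivity of the results to this approach are investigated using a sensitivity analysis in section 4.2.5.5". SAP 4.2.8.3 repeats this for #6: "no adjustment is made for dropout but the sensitivity of the results to this approach are investigated using a sensitivity analysis in section" 4.2.5.5.
- **The analyses pointed to.** SAP 4.2.5.5 lists three: a covariate-adjusted negative binomial model (if numbers allow), the MCC, and the per protocol set. Only the MCC is tied to loss. It is run "if a greater than 10% difference by treatment arm in the proportion who are lost to follow-up is observed", and "The recurring event in this analysis will be hospital admission with HK as a contributing factor". SAP 4.2.8.5 applies the same list to #6.
- **MCC code.** SAP 7.2 describes its outcome input as "The outcome variable, with 0 for censoring, 1 for the event of" interest, with higher codes for competing risks.
- **Elsewhere.** SAP 4.2.3.5 plans inverse probability weighting (IPW) for loss in the time-to-event analysis of #1. Sections 4.2.4.5 and 4.2.7.5 carry it to #2 and #5. Section 4.2.5.5 does not refer to it.

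**The concern.** Both count endpoints are in the formal testing hierarchy, at positions 4 and 7 of SAP Table 5. The trial is open-label and the protocol allows for 20% drop-out after randomisation. The estimand follows participants after they stop treatment, so what happens after loss belongs to the target even though it is not observed. A reader of 4.2.5.3 would expect 4.2.5.5 to show whether the rate ratio survives a departure from ignorable loss. If the analysis there makes the same assumption about loss as the main model, agreement between the two says nothing about that. If it also runs only when loss differs between arms, there will often be no such comparison. A significant rate ratio could then be reported as robust to dropout when this had not been examined.

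**Working it through.** **1. The plan's own numbers.** Protocol 9.2.2 gives a hazard ratio of 0.329, event proportions of 17% and 43.2%, 5% significance and 80% power.
- Hazard ratio: ln(0.83)/ln(0.568) = 0.329.
- Events by Freedman's formula: (1.96 + 0.84)² × [(1 + 0.329)/(1 − 0.329)]², which rounds up to 31.
- Mean event proportion (0.17 + 0.432)/2 = 0.301, and 31/0.301 = 103.0, or 51.5 per arm, rounded to 52.
- 104/0.8 = 130 randomised, and 130/0.8 = 162.5, rounded to 163 enrolled.

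All four stated figures (52, 104, 130, 163) reproduce. With 1:1 allocation there are about 65 per arm. Neither #3 nor #6 has a power calculation of its own.

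**2. What the MCC assumes about loss.** SAP 4.2.5.1 censors at loss, and SAP 7.2 gives censoring code 0. The macro in 7.1 subtracts censored participants from the risk set and goes on. No weight, imputation or delta is applied anywhere in 7.1 or 7.2. That a lost participant receives code 0 is an inference from these sections together; the SAP does not say it in one line.

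**3. Whether it could reveal informative loss.** A large simulation was run with a true rate ratio of 1.00 and 20% loss in each arm. The gamma frailty (variance 1), 0.6 events per 180 days and the loss mechanisms are assumptions. Death was not modelled.

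| Loss mechanism | Negative binomial ratio | MCC ratio |
|---|---|---|
| Non-informative in both arms | 1.01 | 1.00 |
| Proportional to frailty, both arms | 1.00 | 1.00 |
| Proportional to frailty, one arm only | 0.91 | 0.89 |
| Proportional to frailty squared, one arm only | 0.83 | 0.81 |
| Opposite mechanisms in the two arms | 0.88 | 0.85 |

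The two methods move together, so comparing them does not expose the bias.

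**4. How often the trigger is met.** Take X₁, X₂ ~ Bin(65, p) and compute P(|X₁ − X₂|/65 > 0.10). Since 0.10 × 65 = 6.5, this needs a difference of at least 7 participants.

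| True loss, both arms | Probability MCC runs |
|---|---|
| 10% | 0.057 |
| 15% | 0.109 |
| 20% | 0.153 |
| 25% | 0.187 |

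With unequal true loss of 15% v 25% it is 0.50. These figures read the 10% as an absolute difference. Read as relative, the probability at 20% loss is about 0.75 to 0.76, depending on which arm is the base.

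**5. Which event is counted.** The MCC in 4.2.5.5 counts hyperkalaemia-related admissions. Endpoint #3 counts admissions for any cause plus hyperkalaemia-related ED visits. Carried to #6 by cross-reference, the MCC still omits the ED visits.

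**6. Illustrative size.** Let m be the share of SZC person-time that is unobserved, and suppose lost SZC participants have the SoC rate afterwards. Then the full-period ratio = observed × (1 − m) + m. If 20% are lost evenly over 180 days, m = 0.20 × 0.5 = 0.10.
- Observed 0.38 (assumed): 0.38 × 0.9 + 0.1 = 0.442.
- Observed 0.39, borrowing 17/43.2 = 0.39 as a stand-in: 0.39 × 0.9 + 0.1 = 0.451.

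The plan gives no rate ratio for #3, so both starting values are illustrative.

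**The case against.** The best defence is that loss is not ignored, and much of it stands.

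- **Other analyses bear on loss.** The adjusted negative binomial model in 4.2.5.5 has no loss trigger. Endpoint #2 is the time-to-first version of #3, and #5 of #6. Both inherit the untriggered IPW analysis, which uses treatment and eight baseline variables. A reader might infer that no dropout analysis exists when the MCC does not run; the documents do not support that. However, these analyses handle only loss explained by baseline covariates, and the IPW is not applied to the counts.
- **The MCC and its trigger have a rationale.** The offset model assumes a constant event rate; the MCC does not, and it can treat death as competing. If events cluster early, unequal loss distorts the offset model even when loss is non-informative. In a simulation with half of events in the first 30 days (assumed) and a true ratio of 0.50, the negative binomial ratio was 0.525 with 30% v 10% loss, 0.475 with 10% v 30%, and about 0.50 with 20% in each arm. The MCC is a useful check, but of a different question.
- **Equal loss need not bias.** A reader might infer that equal loss is as harmful as unequal loss. Nothing here shows that: the same mechanism in both arms left the ratio at about 1.00. Bias at equal loss needs mechanisms that differ by arm.
- **20% is a planning allowance, not a forecast of loss.** Treatment discontinuers stay in follow-up, protocol 7.2 expects withdrawal to be uncommon, and chart review supplements visits. Protocol 7.3 also records consent withdrawal separately from loss to follow-up. Lower loss shrinks the bias, but under the absolute reading it also makes the trigger rarer.
- **The SAP adds to the protocol.** For these endpoints protocol 9.4.3.2 plans only the per protocol set and the multivariable model. That is true, but 4.2.5.3 and 4.2.8.3 still promise a check that is not delivered.

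**Conclusion.** The point holds in this limited form. For #3 and #6 the stated dropout check does not test outcome-related loss, because the MCC shares the main model's assumption that loss is independent of outcome. On an absolute reading of the trigger it would run in about 15% of trials at 20% loss in both arms and 6% at 10% loss. When it did run, it would count a narrower event than the endpoint. The remaining gap is loss related to outcome beyond the listed baseline covariates.

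The illustrated shift, from 0.38-0.39 to 0.44-0.45, rests on assumed even loss of 20% and reversion to the SoC rate. A reader might carry the formula to 0.50 (0.38 × 0.8 + 0.2 = 0.504), but that needs every loss to fall on day 1 and should not be used as the expected size. The direction and size of any actual bias cannot be known from the documents.

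**What to change.** 1. Remove the 10% trigger from 4.2.5.5. This also removes the absolute-or-relative ambiguity.
2. Make the MCC count each endpoint's own event. Describe it as a check on death as a competing event and on the constant-rate assumption, not as a dropout check.
3. For #3 and #6, pre-specify one dropout analysis that is always run. Extend the IPW of 4.2.3.5 to the count models, and add multiple imputation of post-loss counts in which lost SZC participants take the SoC rate, with a delta range around that.
4. Point 4.2.5.3 and 4.2.8.3 to this analysis.

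The cost is SAP text and one extra program. Trial conduct, sample size and the main analyses do not change. The downside is additional output that may be less favourable to SZC.

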#### **4.2.5.2 Derivations**

For each participant the total number of separate all-cause hospital admissions or ED visits with HK as a contributing factor up to 180 days will be calculated. Hospital admissions and ED visits will be calculated as separate admissions if start and stop dates of admission do not overlap. If hospital admissions or ED visits are missing a start, stop date or both then they will be calculated as separate admissions. Hospital admissions or ED visits started after 180 days will not be counted.

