#### **4.2.8.5 Sensitivity Analyses of the Secondary Endpoint #6**

Sensitivity analyses of this secondary endpoint will be performed as per section 4.2.5.5.

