##### **4.2.14.1 Definition**

- Population: Full analysis set
- Endpoint: Number of hospital admissions with HK as a contributing factor, at any time post-discharge up to 180 days.

- Intercurrent event strategy: Participants who discontinue treatment, use rescue therapy for HK, have RAASi down-titration (including discontinuation), experience all-cause death or loss to follow-up prior to 180 days post-discharge will have all available hospital admission and ED visit data used irrespective of the intercurrent event (treatment policy strategy).
- Population level summary: Mean number of hospital admissions with HK as a contributing factor, by randomised treatment group will be summarised. Negative binomial regression model with randomised treatment group as a main effect and including duration of time in study as an offset. The incidence rate ratio (SZC/SoC), along with 95% confidence intervals and two-sided p-values will be displayed.

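### The mean cumulative count dropout check for secondary endpoints #3 and #6 counts only hospital admissions with hyperkalaemia, an event that matches exploratory endpoint #6 instead

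*SAP*

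**What the plan says.** - **Secondary #3.** SAP 4.2.5.1 defines the outcome as "Number of all-cause hospital admissions or ED visits with HK as a contributing factor at any time post-discharge up to 180 days". Section 4.2.5.2 derives it the same way, and 4.2.5.4 models that count by negative binomial regression with time in study as an offset.
- **Dropout.** On the primary analysis, SAP 4.2.5.3 says: "no adjustment is made for dropout but the sensitivity of the results to this approach are investigated using a sensitivity analysis in section 4.2.5.5".
- **The sensitivity analyses.** SAP 4.2.5.5 lists three: a covariate-adjusted negative binomial model, the MCC analysis, and a repeat in the per protocol set. The MCC analysis is run only "if a greater than 10% difference by treatment arm in the proportion who are lost to follow-up is observed". It reports estimates by arm at 90 and 180 days, and it fixes the event: "The recurring event in this analysis will be hospital admission with HK as a contributing factor". For the method it cites the paper on absolute risk reductions.
- **Secondary #6** (SAP numbering; #5 in Protocol 9.4.3.2) counts admissions and ED visits, both with HK. SAP 4.2.8.3 points to 4.2.5.5 for dropout, and 4.2.8.5 says: "Sensitivity analyses of this secondary endpoint will be performed as per section 4.2.5.5".
- **Exploratory #6.** SAP 4.2.14.1 defines the endpoint as "Number of hospital admissions with HK as a contributing factor, at any time post-discharge up to 180 days". Section 4.2.14.5 carries the same sentence on the recurring event, and cites the mean cumulative count paper.
- **Protocol.** Section 9.4.3.3 places the MCC analysis under exploratory #6. For the two secondary counts, 9.4.3.2 lists only the per protocol repeat and a multivariable negative binomial model.

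**The concern.** A sensitivity analysis for dropout should keep the endpoint fixed and change only how incomplete follow-up is handled. Here the endpoint changes as well. If the MCC result differed from the primary rate ratio, nobody could tell whether dropout or the narrower event was the reason. If it agreed, the agreement would say little about the all-cause count.

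Both secondary counts are in the formal testing order (SAP Table 5, orders 4 and 7). The trial is open-label and plans for 20% drop-out after randomisation (Protocol 9.2.2). The trigger, unequal loss between arms, is the situation in which a matching check is most needed. If the text stays as it is, the event would have to be reinterpreted after the imbalance has been seen.

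**Working it through.** No figure stated in the plan is in dispute, so the main check compares the texts.

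**Step 1. What each endpoint counts, against the MCC event (admissions with HK).**

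| Endpoint | Admissions with HK | Admissions without HK | ED visits with HK | Left out by the MCC event |
|---|---|---|---|---|
| Secondary #3 (SAP 4.2.5.1, 4.2.5.2, 4.2.5.4) | counted | counted | counted | admissions without HK; HK ED visits |
| Secondary #6 (SAP 4.2.8.1, 4.2.8.2) | counted | not counted | counted | HK ED visits |
| Exploratory #6 (SAP 4.2.14.1) | counted | not counted | not counted | nothing |

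The MCC event fits exploratory #6 exactly, secondary #6 in part, and secondary #3 least.

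**Step 2. Could another analysis in 4.2.5.5 serve as the dropout check?** The covariate-adjusted model and the per protocol repeat do use the #3 count, but neither is tied to loss to follow-up. Only the MCC analysis is.

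**Step 3. Is a narrower event justified anywhere?** Protocol 9.4.3.2 has a sensitivity analysis that restricts admissions to those with HK. It belongs to secondary #1 and is carried by reference to other time-to-event endpoints. It is not listed for #3, and it would not serve the purpose stated in SAP 4.2.5.3.

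**Step 4. Can the size be computed?** It would need the share *s* of admissions in which HK contributed, and neither document gives it. The nearest inputs are the planning assumptions in Protocol 9.2.2: all-cause hospitalisation 16.2% (SZC) and 40% (SoC), HK ED visits 0.8% and 3.2%, added to 17% and 43.2%, with 52 evaluable participants per arm.

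- Participants with an event of the #3 type: 52 × 0.17 + 52 × 0.432 = 8.8 + 22.5 = 31.3.
- Participants with an HK admission, assuming the same *s* in both arms: *s* × 52 × (0.162 + 0.40) = *s* × 29.2.
- For *s* = 10%, 25%, 50%, 75% and 100%, this gives 2.9, 7.3, 14.6, 21.9 and 29.2 participants, or 9%, 23%, 47%, 70% and 93% of 31.3.

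The range is too wide to support a figure. These inputs are also proportions of participants with an event, whereas MCC counts repeat events. The one firm result is that even at *s* = 100% the match is incomplete, because HK ED visits are missing.

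**Step 5. The appendix macro (SAP 7.2).** The first-event data set keeps the time variable as supplied. For second and later events the loop recomputes it as (event date − start date)/365.25. All sets are then stacked, sorted on that variable and summed. The parameter notes give no unit.

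- Supplied in years: all events share one unit and there is no error.
- Supplied in days: a later event on day 180 gets 180/365.25 = 0.49 and sorts ahead of a first event on day 1. The 90-day estimate would then include repeat events from days 91 to 180.

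**The case against.** **The analysis is conditional and descriptive.** This stands. It produces estimates by arm and alters neither the negative binomial tests nor the testing order. The trigger may well not be met. As an illustration, assume 20% loss in both arms, 130/2 = 65 participants per arm, and read 10% as percentage points. The standard error of the difference is √(2 × 0.2 × 0.8/65) = 0.070, so a gap above 0.10 arises by chance about 15% of the time. Truly unequal loss would raise that figure.

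**No protocol commitment is breached.** This also stands, since the protocol asks for MCC only under exploratory #6. But SAP 4.2.5.3 and 4.2.8.3 themselves rely on 4.2.5.5 for dropout, so the gap lies within the SAP.

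**Stronger readings that a reader might infer, and that the documents do not support:**

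- *Most of the endpoint is dropped.* Any percentage depends on an assumed HK share and treats proportions of participants as event counts (Step 4).
- *The MCC result would say nothing about secondary #6.* HK admissions are a component of that endpoint, and only the HK ED visits are missing.
- *The macro is wrong.* It misplaces events only if time is supplied in days, and the SAP does not say which unit is used.
- *The text was copied by mistake.* The identical sentence in 4.2.14.5 and the misplaced citation make this plausible, but it remains an inference.

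**Conclusion.** The point holds, with limited reach. As written, SAP 4.2.5.5 provides no dropout check that matches secondary #3, and only a partial one for secondary #6. This follows from the definitions alone and needs no numerical assumption. The primary analyses and the other two sensitivity analyses of both endpoints are unaffected. The loss matters only if the trigger for unequal loss to follow-up is met, and its size cannot be derived from the documents. The citation for the method in 4.2.5.5 is a plain slip. The macro's time unit is an unstated input requirement and not a demonstrated error.

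**What to change.** - **SAP 4.2.5.5:** set the recurrent event for secondary #3 to any hospital admission, whatever its cause, or any ED visit to which HK contributed.
- **SAP 4.2.8.5:** give secondary #6 its own recurrent event, a hospital admission or an ED visit, each with HK contributing.
- **SAP 4.2.14.5:** keep the present sentence here only.
- **Citation in 4.2.5.5:** replace the absolute-risk-reduction paper with the mean cumulative count paper already listed in SAP section 6.
- **Macro in SAP 7.2:** state that the time variable must be supplied in years, or compute it from the dates in the same way for first and later events.

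The cost is SAP wording and at most one line of code. No new data are needed, since the endpoint derivations already use both admissions and HK ED visits. The change should be made before database lock, the limit that Protocol 9.4 sets for SAP changes.
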